### **Interim analyses**

No formal interim analyses are planned. The TSC will monitor event (nAMD conversion) data and also the disagreement between tests (blinded to individual test results and differences) to evaluate the key assumption in the sample size calculation. A single final set of analyses is planned once the study has recruited and data has matured.

### **Time points of outcome collection**

In order to assess the sensitivity and specificity of the diagnostic tests under evaluation, each of the diagnostic tests being assessed will be performed on the study eye at each routine clinic visit during the period of follow up.

Results from the diagnostic tests according to the definitions will be recorded on a standardised case report form. If any diagnostic tests are positive this will trigger the request for an FFA and the absence/presence of nAMD (and classification) will be recorded. These data will be uploaded to the study website by study staff.

**Table 1 Timing of outcome collection**

Assessment	Recruitment	Routine visits (approx. every 8 weeks)	If any diagnostic test positive	If FFA positive	18 months	exit
Assessment of eligibility criteria	✓					
Written informed consent	✓					
Baseline vision and risk factors	✓					
Blood collection	✓			✓		✓
Diagnostic tests: 
 
• Subjective patient vision
 
• AMSLER
 
• Visual acuity
 
• OCT
 
• Fundus examination
 
• Autofluorescence (only if available)
 
	✓	✓			✓	✓
Reference standard: FFA	✓		✓		✓	✓
Post conversion case note review						✓
Upload of required imaging to reading centre for analysis	✓		✓		✓	✓

## **Eligibility**

Patients with newly diagnosed nAMD in one eye and an unaffected second eye (study eye).

Inclusion criteria:

- Newly diagnosed nAMD in one eye and an unaffected second eye (diagnostic FFA to be within 6 weeks prior to consent)
- About to commence or recently commenced anti VEGF therapy in the first eye
- Age 50 -95

Exclusion criteria:

- patients with a history of nAMD in both eyes;
- nAMD in study eye detected at baseline;
- presenting visual acuity worse than 68 letters;
- retinal pathology in the study eye which can confound subsequent assessments (e.g. diabetic retinopathy, macular hole);
- not undergoing regular monitoring in standard of care;
- patients who cannot give informed consent;
- unable to undergo a fundus fluorescein angiography (FFA) test;
- patients whose baseline FFA was more than 6 weeks ago

## **Change of status**

Participants will remain in the study unless they choose to withdraw consent or if they are unable to continue for a clinical reason. All changes in status with the exception of complete withdrawal of consent will mean the participant is still followed up for all study outcomes wherever possible. All data collected up to the point of complete withdrawal will be retained and used in the analysis unless the participant requests this to be destroyed and excluded. If the participant had previously consented to and donated blood for storage, and the participant later withdraws consent, they may also request for their donated blood to be destroyed.

## **Baseline patient characteristics**

Table 1 of the dummy tables outlines the baseline characteristics which will be collected and summarised.

## **Outcomes**

### **Primary outcome measure**

The **primary diagnostic performance outcomes** will be the sensitivity and specificity of the index tests on detection of nAMD in the study eye in a monitoring setting.

The **primary economic outcome** will be the incremental costs (to the health service) per quality adjusted life year (QALY) gained.

### **Secondary outcome measure**

Secondary diagnostic performance outcomes will include diagnostic odds ratio, likelihood ratio, and proportion of indeterminate tests. The performance of combinations of tests will be evaluated.

Other outcomes: time gain of early detection, visual acuity at diagnosis, performance of a risk predictor algorithm according to baseline characteristics, the establishment of a well characterised cohort of clinical and biological data for future research.

## **Analysis**

- **Analysis objectives**

1. Determine the diagnostic monitoring performance of the interventions (ETDRS visual acuity; fundus evaluation of signs of nAMD; the Amsler test; clinical assessment of images captured by OCT; patient's subjective assessment of vision) against the reference standard of fundus fluorescein angiography.
2. Develop a risk prediction model using baseline characteristics to predict the development of nAMD in the study eye
3. Quantify the time to diagnosis and risk of conversion
4. Explore the impact of CNV subtype on time to conversion

- **Method**

Participants are categorised as nAMD or not nAMD according to the presence of a positive FFA result (as assessed by the responsible ophthalmologist) during the follow-up period. To address the analysis objectives, the following analyses are planned:

## **Analysis Objective 1: Determine the diagnostic monitoring performance of the interventions**

### **Analysis A. Person level diagnostic accuracy analysis.**

**Table 3** outlines the different definitions for the reference standard and an index test positive result for all the analysis under the person level diagnostic accuracy analysis.

Under the main analysis approach (analysis A1, see **table 3**), repeated monitoring test assessments are collapsed over time to give a single candidate test result (positive or negative). This is compared with a single final local FFA result from the participant. Other approaches will be considered by varying the definitions for reference standard and index tests included in the analysis (analysis A2 – A7, see **table 3**).

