### **Participant inclusion criteria for analysis A**

For each of the 5 index tests, the following criteria will be applied separately:

1. Last FFA result shows no nAMD:

The participant will be included if there is **at least one prior** index test result during the follow-up period.

2. Last FFA result shows nAMD:

The participant will be included if there is an index test result within the previous 3-months. If a participant does not have an index test result within the previous 3-months of their last FFA the FFA will not be considered valid and we will look for an earlier FFA result for the participant and apply rules 1 and 2 again on the earlier FFA.

If no follow-up FFA is available which satisfies either criteria, then the participant will be excluded. If no follow-up FFA is available, the participant will be excluded from the analysis.

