### **Definition of valid follow-up period**

If a participant is included as defined above, then the valid follow-up period will be from baseline until the date of the last valid FFA (as defined above).

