**Table 2 Two by two table: definitions of test and disease status.**

	Index positive	Index negative
Reference standard positive: nAMD	True positives Any reference standard indicates nAMD in study eye AND Any index test result is positive during valid follow-up period	False negatives Any reference standard indicates nAMD in study eye AND Index test negative for all available prior time points
Reference standard negative: No nAMD	False positives All reference standard results indicate no nAMD in study eye AND Any positive index test result during valid follow-up period	True negatives All reference standard results indicate no nAMD in study eye AND Index test negative for all available prior time points

Sensitivity and specificity will be calculated with 95% confidence intervals calculated using the Agresti-Coull method (Zhou 2002). Positive and negative likelihood ratios will also be calculated with 95% confidence intervals calculated using the method in Zhou 2002. Diagnostic odds ratios and the proportion of indeterminate tests will be calculated with 95% confidence intervals. A ROC curve will be plotted and the area under the ROC curve calculated using the trapezoidal rule for visual acuity tests. The standard error for the AUC will be calculated using the method of DeLong, DeLong and Clarke-Pearson (1998) and used to form an asymptotic normal 95% confidence interval.

Monitoring sensitivity and specificity of the tests will be compared using McNemar's statistical test (with 95% confidence intervals produced using Newcombe's method) (Newcombe 1998).

For comparing sensitivities under the primary analysis, the McNemar 2x2 table will be constructed using only patients who have had a positive FFA result. They will be classified as having a positive index test, if the index test has any positive results during the valid follow-up period. They will be classified as having a negative index test, if all prior available tests have been negative during their valid follow-up period. For comparing specificities under the primary analysis, the McNemar 2x2 table will be constructed using only patients who have had negative FFA results throughout using the same index test classification.

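### Analysis A1 sets disease status by the last valid FFA, judged per index test, in one place and by any positive FFA in another, with no rule for McNemar pairs whose valid FFAs differ

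*SAP*

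**What the plan says.** For A1 the SAP fixes the reference status of the study eye in two ways.

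**Last valid FFA, per test.** The opening of Analysis A says of the collapsed index result: "This is compared with a single final local FFA result from the participant". The inclusion criteria that follow begin: "For each of the 5 index tests, the following criteria will be applied separately". If the last FFA shows nAMD but the test in question has no result in the 3 months before it, "the FFA will not be considered valid and we will look for an earlier FFA result for the participant". Without any qualifying FFA, "If no follow-up FFA is available which satisfies either criteria, then the participant will be excluded". For those kept, "the valid follow-up period will be from baseline until the date of the last valid FFA". The missing-data section adds that an eye with no positive reference result inside the valid period is taken as negative.

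**Any positive FFA.** The Method paragraph classifies participants "according to the presence of a positive FFA result (as assessed by the responsible ophthalmologist) during the follow-up period". Table 2 defines a true positive as: "Any reference standard indicates nAMD in study eye AND Any index test result is positive during valid follow-up period". There the validity limit applies to the index test and not to the reference standard. For comparing sensitivities, "the McNemar 2x2 table will be constructed using only patients who have had a positive FFA result"; for specificities, only patients whose FFAs were all negative. Definition A, given before Table 3 and again under Sensitivity analyses, is likewise positive on any nAMD finding and negative only if there was none.

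**The concern.** For most eyes the two rules agree. Under Protocol 3.6.6 and 3.6.7 a positive FFA leads to a clinical diagnosis and monitoring stops, so the positive FFA is normally also the last one.

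They part when the 3-month rule sets aside a positive FFA for one test and an earlier negative follow-up FFA is valid for that test. The earlier FFA may be the 18-month one or a negative triggered one. The inclusion criteria and the missing-data section then make the eye no nAMD for that test. Table 2, the McNemar text and definition A, followed as written, still make it nAMD. They judge the test on results up to the earlier FFA, so a test with no positive by then is charged with missing a conversion that happened after its window closed.

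The eyes concerned are converters, who form the smaller side of the primary comparison. Two programmers could follow the SAP correctly and produce different 2x2 tables. Validity is judged per test, so the two tests in a McNemar comparison can also have different valid FFAs and different windows, and the SAP does not say how that pair is formed.

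**Working it through.** **Inputs.** From the SAP, Sample size: 491 participants before inflation, 28% cumulative incidence, sensitivities of 80% and 65%, disagreement ψ = 0.30, two-sided 5%, 90% power, lower specificity 87%. From the SAP inclusion criteria: the 3-month rule, taken as 91 days or 13 weeks. From Protocol 1.1 and 3.2: visit spacing. Assumed, because the documents give no figure: the number k of set-aside converters.

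**1. The plan's own figure.** With d = 0.15, converters needed = [1.96√ψ + 1.2816√(ψ − d²)]² / d² = [1.96√0.30 + 1.2816√0.2775]² / 0.0225 = 135.9, so 136. Then 136 / 0.28 = 485.7, so 486 against the stated 491 (1.0% apart). Dividing 491 by 0.88 gives 558, in line with 560. The sample size is sound and is not at issue. It implies 491 × 0.28 = 137 converters and 491 − 137 = 354 non-converters.

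**2. One participant traced through the rules.** FFA negative at day 548 (about month 18) and positive at day 800. Test X was done at day 800. Test Y was last done at day 672, which is 128 days before the positive FFA, and was never positive.

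| Rule | Test X | Test Y |
|---|---|---|
| Inclusion criteria and valid period | valid FFA day 800: nAMD | valid FFA day 548: no nAMD |
| Table 2, McNemar text, definition A | nAMD | nAMD |

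Y is a true negative under the first row and a false negative under the second. If there had been no negative FFA at day 548, the participant would be excluded for Y. The statuses would not conflict, but the X–Y pair would still be incomplete.

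**3. When the rule can bite.** If one result is missed at the conversion visit, the last result is one visit interval older. The FFA then fails the rule if it follows that visit by more than:

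- 12-weekly visits (upper end for year 2, Protocol 3.2): 13 − 12 = 1 week
- 8-weekly visits: 13 − 8 = 5 weeks
- about 8 visits a year (year 2, Protocol 1.1; 52 / 8 = 6.5 weeks): 13 − 6.5 = 6.5 weeks
- 35-day mean interval (year 1, Protocol 1.1): 13 − 5 = 8 weeks

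Two results missed in a row at 8-weekly visits (16 weeks) fail it outright.

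**4. Size, for assumed k of 1 and 3.** Keep the k eyes as nAMD, as Table 2 does.

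- Y negative in the shortened window: sensitivity = 0.65 × (137 − k) / 137.
- Y positive in the shortened window, for instance because Y triggered the earlier negative FFA: sensitivity = [0.65 × (137 − k) + k] / 137.
- Eyes counted as no nAMD for Y, with Y negative: specificity = (0.87 × 354 + k) / (354 + k).

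| Quantity | k = 1 | k = 3 |
|---|---|---|
| Sensitivity, Y negative in window | 64.5% (−0.5) | 63.6% (−1.4) |
| Sensitivity, Y positive in window | 65.3% (+0.3) | 65.8% (+0.8) |
| Sensitivity, eyes excluded or counted no nAMD | 65.0% of 136 | 65.0% of 134 |
| Specificity, eyes counted no nAMD (from 87.0%) | 87.04% | 87.11% |

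**5. Power if such pairs are dropped.** Φ[(d√n − 1.96√ψ) / √(ψ − d²)] is 90.2% at n = 137 and 89.6% at n = 134.

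**The case against.** The strongest reply is that the SAP, read as a whole, already answers the question. A set-aside FFA is declared not valid, the follow-up period is built on valid FFAs, and the missing-data section presumes a negative when no positive falls in that period and speaks of a curtailed period. On that reading Table 2 is only a summary. This stands as evidence of intent, but it does not remove the conflict: Table 2, the McNemar text and definition A carry no such limit on the reference standard. Nor does it supply a pairing rule, since the presumption applied per test can give different answers for the two tests.

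It is also fair to say that the route is narrow. All index tests are scheduled at routine visits, FFAs are triggered there or done alongside the tests at 18 and 36 months, and a missed visit removes every test together. The one systematic gap, Amsler testing stopped after distortion at baseline (Protocol 3.2.4), leaves no follow-up Amsler results, so those participants are excluded for Amsler without conflict.

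A reader might infer that the plan puts a participant into one McNemar table as diseased for one test and healthy for the other. It does not. The McNemar text taken alone gives each table a single disease status; the split appears only when the two rules are mixed. A reader might also infer a sizeable bias in one direction. That would need many set-aside eyes, always negative on the affected test, and the documents support neither assumption.

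**Conclusion.** The SAP holds two reference-status rules for its primary analysis. In one identifiable situation the rule in Table 2 and the McNemar text, applied as written, scores a test on a window that ended before conversion. How to pair tests with different valid FFAs is not stated. This is more than missing detail, but its likely effect is small: about 0.5 to 1.4 points lower sensitivity for the affected test with 1 to 3 such eyes. That rests on 137 converters, 65% sensitivity and a negative result in the shortened window. If that test had triggered the earlier false-positive FFA, the shift is upward, by 0.3 to 0.8 points on the same figures. The true number of set-aside eyes is not in the documents, and no overall bias is claimed. Ordinary converters and the sample size are unaffected. The case for acting is that the choice between the rules should be settled before the results are seen.

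**What to change.** In Table 2, the McNemar text and both statements of definition A, limit the reference status to valid local FFAs within the valid follow-up period: nAMD if any of them is positive, no nAMD if all are negative. Align the sentence on the single final FFA at the start of Analysis A with this. Analysis B also uses definition A, so say that the limit belongs to Analysis A, for which the validity criteria are written.

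In the McNemar text, state that each comparison uses only participants whose FFA is valid under the inclusion criteria for both tests, over one common window, and that others are excluded from that pair.

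Report the number of positive FFAs set aside for each index test. The Method paragraph, which introduces all four objectives, can stay as it is, and no extra sensitivity analysis is needed.

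The cost is SAP wording and one set of counts, with no new data. A few converters may leave some pairs; losing 3 of 137 would move the design power from 90.2% to 89.6%.

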### **Participant inclusion criteria for analysis A**

For each of the 5 index tests, the following criteria will be applied separately:

1. Last FFA result shows no nAMD:

The participant will be included if there is **at least one prior** index test result during the follow-up period.

2. Last FFA result shows nAMD:

The participant will be included if there is an index test result within the previous 3-months. If a participant does not have an index test result within the previous 3-months of their last FFA the FFA will not be considered valid and we will look for an earlier FFA result for the participant and apply rules 1 and 2 again on the earlier FFA.

If no follow-up FFA is available which satisfies either criteria, then the participant will be excluded. If no follow-up FFA is available, the participant will be excluded from the analysis.

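### A converter with no result on one index test in the 3 months before the positive FFA can be analysed as no nAMD for that test but nAMD for the others

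*SAP*

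**What the plan says.** The rule is in the SAP under Participant inclusion criteria for analysis A: "For each of the 5 index tests, the following criteria will be applied separately". When the last FFA shows no nAMD, one earlier follow-up result of the test is enough. When it shows nAMD, the condition is stricter: "The participant will be included if there is an index test result within the previous 3-months". If that fails, "the FFA will not be considered valid and we will look for an earlier FFA result for the participant", and the analyst is to "apply rules 1 and 2 again on the earlier FFA". There is also an exit: "If no follow-up FFA is available which satisfies either criteria, then the participant will be excluded".

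The next section ties the observation period to the outcome of this search: "the valid follow-up period will be from baseline until the date of the last valid FFA". The section on missing data presumes a negative status when no positive FFA lies in the valid period, and it refers to a curtailed period, so the truncation is intended.

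Other parts of the SAP define status per person. The Method paragraph classifies participants by whether a positive local FFA occurred during follow-up. Table 2 reserves the no-nAMD row for participants in whom "All reference standard results indicate no nAMD in study eye". For comparing sensitivities, "the McNemar 2x2 table will be constructed using only patients who have had a positive FFA result"; for specificities, only participants with negative FFAs throughout are used.

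**The concern.** Disease status in an accuracy study should not depend on whether the test under evaluation happened to be recorded. Here it can. The 3-month condition applies only to positive FFAs, so only converters can be reclassified. The rule runs test by test, so the same eye can be a case for OCT and a non-case for the Amsler test.

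Three things are at stake in the primary analysis (A1). Some participants with a positive FFA may sit in a test's specificity denominator. The five tests may be judged on different case sets. The McNemar comparisons may not match the single-test tables, because nothing says how to pair a participant who has one status for one test and another for the second. None of the six listed sensitivity analyses examines the rule.

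**Working it through.** **Tracing one participant through the rules.** Take a participant with a negative FFA at 18 months and a positive triggered FFA in year 3. OCT was done in the 3 months before it. The last recorded Amsler result is older than that, and there are Amsler results before 18 months.

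- OCT: the positive FFA is valid. Status is nAMD, and follow-up runs to the positive FFA.
- Amsler: the positive FFA is set aside. The 18-month FFA is negative and has a prior Amsler result, so the participant enters as no nAMD. Valid follow-up ends at 18 months.
- Method paragraph, Table 2 and McNemar text, read literally: nAMD for both tests.
- OCT v Amsler pair: no instruction.

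If the participant had no earlier follow-up FFA, or no Amsler result before it, the outcome for Amsler would be exclusion. Protocol 3.6.7 ends monitoring at a clinical diagnosis of nAMD, so an earlier FFA is ordinarily negative. It is either the 18-month FFA or a negative triggered one.

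**The plan's own sample size.** Inputs from the SAP, Sample size: difference d = 0.15, disagreement psi = 0.30, two-sided 5%, 90% power, incidence 28%, N = 491.

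- n = (1.96 x sqrt(psi) + 1.2816 x sqrt(psi - d^2))^2 / d^2 = (1.0735 + 0.6751)^2 / 0.0225 = 135.9, so 136 converters.
- 136 / 0.28 gives N = 486. The simpler variant, (1.96 + 1.2816)^2 x psi / d^2, gives 141 converters and N = 504. Both are within 3% of 491.
- Expected converters: 491 x 0.28 = 137. Non-converters: 491 - 137 = 354. Power with 137 converters is 0.902.

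**Size of the problem.** The documents give neither the share m of converters without a given test in the window nor the share f of those with a qualifying earlier negative FFA. Assumed ranges: m = 5-20%, f = 30-70%.

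- Leave the test's sensitivity denominator: 137 x 0.05 = 7 to 137 x 0.20 = 27.
- Enter its no-nAMD group: 6.85 x 0.30 = 2 to 27.4 x 0.70 = 19. The remainder are excluded for that test.
- Relative to the 354 non-converters: 19/354 = 5.4%. As a share of the enlarged group: 19/373 = 5.1%.
- Specificity, starting from the SAP's 94% in 354 (332.76 negatives). With 2 added: 332.76/356 = 93.5% if both are index-positive, 334.76/356 = 94.0% if both are negative. With 19 added: 332.76/373 = 89.2% to 351.76/373 = 94.3%.

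**McNemar text read literally.** The converter stays in the sensitivity table, but the test is read only to the curtailed date. Only those with a curtailed period are affected, so the outer bound is 19/137 = 14 percentage points, against a 15-point target difference. It is reached only if every such test was negative before the earlier FFA and would otherwise have been positive.

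**The case against.** The strongest defence is that the SAP deliberately works within a valid period. Reference and index results are then assessed over the same interval, and at its end the eye was FFA-negative. For a single test's 2x2 table this is coherent, and that part stands. It does not rescue the paired analysis. The interval still depends on which test was recorded, and the McNemar sets are defined by the participant's FFA results.

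The effect may also be small. Protocol 3.2 expects visits every 4-8 weeks in year 1 and 8-12 weeks in year 2, with the tests done on both eyes each time, and the 18- and 36-month visits repeat the baseline tests alongside FFA. The dummy tables would show missing results per test and the interval from test to FFA. This is fair: no affected count is given, and 5-20% is an assumption. On the other side, follow-up data are extracted from routine records, and at 8-12 week spacing a 3-month window may hold only one or two visits.

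Three stronger readings are tempting but unsupported. A reader might infer that every converter lacking a test becomes no nAMD; the exclusion branch prevents that. Participants whose Amsler results are not collected because of baseline distortion (Protocol 3.2.4), for example, are excluded, not switched. A reader might infer that the test is always scored negative; any positive before the earlier FFA still counts, and a triggered earlier FFA may have been caused by that very test. A reader might put the McNemar distortion at 27/137, or 20 points, above the target difference; that requires all 27 to have a qualifying earlier FFA, which contradicts the 30-70% assumption.

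**Conclusion.** The point holds as an internal conflict in the primary analysis. The inclusion rule makes disease status specific to each test and dependent on index-test availability. The Method paragraph, Table 2 and the McNemar sets define it per person. Different programmers could build different primary tables from the same text.

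The valid-period reading puts about 2-19 FFA-positive participants into a test's no-nAMD group, and the literal McNemar reading moves a sensitivity difference by at most about 14 points. Both figures rest on the assumed m and f, and the real effect may be negligible. The case for correcting the text is that the primary tables cannot be programmed consistently as written, not that a large bias has been shown.

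**What to change.** Set disease status once per participant from the local FFA (any positive during follow-up is nAMD), independently of index-test availability. Do not replace a positive FFA with an earlier negative one. If a converter has no result on a test in the 3 months before the positive FFA, treat that test as missing for its own 2x2 table and its McNemar pairs. Build each pair only from participants with both tests valid and one common status. Report the number affected per test. Add bounds that score those tests all negative, then all positive: with 80% sensitivity in the retained converters, these span 76-81% at 5% missing and 64-84% at 20%. Align the inclusion criteria, valid follow-up definition, Method paragraph, Table 2, McNemar text and missing-data section.

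The cost is SAP wording, programming and some paired converters. With one test missing in 5, 10 or 20% of the 137, about 130, 123 or 110 pairs remain, with power about 0.89, 0.87 or 0.83 for the 15-point difference. If both tests are missing independently at those rates, power is about 0.87, 0.83 or 0.74. The 12% allowance behind the 560 target may absorb part of this. The single-test sensitivity denominators are no smaller than under the present rule.
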